9.1 Overview

Participants will be assigned to one of two treatment groups: 1) PUSH or 2) PULSE. The PUSH intervention group will receive a specific multi-component training intervention and the PULSE intervention group will receive a non-specific intervention that stimulates the same muscle groups as the PUSH intervention. Both groups will receive 32 visits of approximately 60 minutes duration from a study PT. Participants will receive two visits per week, on non-consecutive days, for 16 weeks. Missed visits can be replaced during subsequent weeks if there is at least one day in between visits and no more than three visits in the week. Visits will take place in the participant's place of residence.

9.2 Nutritional Intervention

Given the importance of ensuring adequate nutrition in both study groups, we will provide all participants with 2000 IU of vitamin D3, 600 mg of calcium, and a multivitamin daily for the duration of the 16-week study and nutritional counseling to ensure weight stability, adequate nutrient intake of 1 g protein/kg body weight inclusive of a healthy diet (50% carbohydrate, 20% protein, 30% fat). Participants will be screened at the time of randomization to assess nutritional risk using the Mini Nutritional Assessment-Short Form (MNA®-SF).⁶ Those who score ≤ 7 (malnourished) at baseline and participants with serum albumin 2.5-3.5 g/dl (regardless of the score on MNA®-SF) will receive a visit from a registered dietician (RD) in their place of residence within seven days of randomization. The RD will evaluate and counsel them on making dietary modifications based on their protein, caloric and other dietary deficiencies using a standardized approach across the three study sites.⁷⁻⁹ The RD will follow up with participants by telephone one week after the visit to assess understanding and implementation of recommendations. Participants who score 8-11 (at risk of malnutrition) at baseline and have serum albumin level >3.5 g/dl will receive a telephone dietary consultation with the RD within seven days of randomization. Based on the participant's eating habits and food intake, the RD may make the clinical determination that an in-person consultation is warranted. In these cases, the RD will schedule an in-person dietary consultation, following the same protocol as those who score in the malnourished range. Those with a score ≥ 12 on the MNA®-SF and who have serum albumin level >3.5 g/dl at baseline will receive brief telephone contact within seven days of randomization from the RD to discuss the importance of calorie and protein intake.

Weight will be monitored during home PT visits every four weeks and those who lose 2% or more body weight in a four-week period will receive another telephone consultation by the study RD. This protocol applies to anyone who loses 2% or more of body weight, regardless of whether the participant is trying to lose weight. In the event that a weight measurement is not obtained at the last PT visit, the participant's weight at the 16-week follow-up assessment will be compared to his or her baseline weight and, if there is weight loss of 5% or more, the clinical site PI or clinical site clinician will review the participant's weight trajectory, baseline BMI, baseline MNA®-SF score, and registered dietician's documentation and, if warranted based on

clinical judgment, will refer the participant to a dietician or medical provider for follow-up of possible poor nutritional status.

Participants randomized prior to version 10.0 of the protocol received vitamin D, calcium, and multivitamin supplements for a total of 40 weeks.

[figure not shown]

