**COMMUNITY AMBULATION FOLLOWING HIP FRACTURE
PROTOCOL (Version 12.0)**

Summary of Modifications to Protocol Version 11.0 for Version 12.0

Version (date)	Section	Brief Summary of Modification
Version 12.0 (10/19/16)	9.2, 10.4.9, 11.2, 12.1.8, Table 2	
Prior to Version 12.0 of the protocol, three strategies were used to address participants' nutritional status: 1) Consultation with a study registered dietician (RD) at baseline for participants who are malnourished (Mini Nutritional Assessment-Short Form (MNA®-SF) score ≤ 7), at risk for malnutrition (MNA®-SF score 8-11), or with serum albumin ≤ 3.5 g/dl; 2) Consultation with a study RD if there is weight loss of 2% or more between weight assessments performed every four weeks in the course of the intervention visits, and 3) Referral for follow-up and/or medical evaluation for possible malnutrition if the MNA®-SF score at follow-up is ≤ 7.
 
In Version 12.0, to streamline procedures, we eliminated the third strategy (MNA screening for malnutrition at follow-up). Identifying nutritional deficiencies at baseline (the first strategy) and monitoring weight loss throughout the intervention period (the second strategy) will be sufficient for addressing participants' nutritional status.
 
In the event that a weight measurement is not obtained at the last PT intervention visit, the participant's weight at the 16-week follow-up assessment will be compared to his or her baseline weight and, if there has been weight loss of 5% or more, the clinical site principal investigator or clinical site clinician will review the participant's weight trajectory, baseline body mass index, baseline MNA®-SF score, and registered dietician's documentation and, if warranted based on clinical judgment, will refer the participant to a dietician or medical provider for follow-up of possible poor nutritional status.

Summary of Modifications to Protocol Version 10.0 for Version 11.0

Version (date)	Section	Brief Summary of Modification
Version 11.0 (8/26/16)	1, 6.1, 8.1, 10, 11	In order to conserve resources, we eliminated several secondary and tertiary outcome measures, while retaining measures needed for the assessment and adjudication of the primary outcome, to determine study eligibility, to ensure participant safety, to monitor adverse events, and to describe characteristics of the participant population.

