10.4.9 Nutritional Status

Nutritional status will be assessed using the Mini Nutritional Assessment-Short Form (MNA®-SF),^{6,192} a validated and widely used malnutrition screening tool.¹⁹²⁻¹⁹⁵ We are using a modified version of the MNA®, approved by the scale's developer (the Nestlé company), to facilitate use as an interviewer-administered tool in a research setting. Scores range from 0 to 14; participants scoring ≤7 will be considered malnourished; those scoring 8-11 will be considered to be at risk of malnutrition; and those scoring 12-14 will be considered to have normal nutritional status.^{6,192}

This measure will not be collected at follow-up for participants consented under protocol version 12.0 or later.

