10.6.2 Weight Loss

Weight will be monitored by the PTs every four weeks during the 16-week intervention period using a standard digital scale.

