12.1.2 Safety Considerations for Study Assessments

All study assessments will be done by certified staff who will be trained to perform the tests safely. If, during the SMWT, the SPPB, or the mPPT, a participant reports chest pain, tightness or pressure, significant shortness of breath or difficulty breathing, or feeling faint, lightheaded, or dizzy, the test will be stopped. All research staff who come in contact with study participants will be CPR certified and will be trained to provide immediate care when faced with medical emergencies. Also, institutional and community emergency medical services will be activated if needed.

Table 2 describes a summary of safety alerts and the appropriate action during clinical assessments.

Table 2. Safety Alerts and Actions for Study Assessments

ALERT	ACTION
Resting blood pressure SBP > 145mm Hg or DBP > 90mm Hg	Qualified staff will inform the participant if noted on more than one occasion.
Resting blood pressure SBP > 170mm Hg or SBP < 90mm Hg or DBP > 100mm Hg or DBP < 50mm Hg	Qualified staff will encourage the participant to seek additional follow-up and/or medical evaluation. Physical performance testing will be deferred until consultation with the study clinician.
Resting blood pressure or after SMWT SBP > 185mm Hg or SBP < 90mm Hg or DBP > 110mm Hg or DBP < 50mm Hg	Qualified staff will consult with the study clinician and follow up as needed.
Resting pulse Rate > 120 or < 40 beats/min	Qualified staff will consult with the study clinician and follow up as needed.
Chest pain, dizziness, significant shortness of breath, or severe musculoskeletal pain during the intervention or study assessment.	Qualified staff will consult with the study clinician and follow up as needed.
CES-D Score \geq 27	Qualified staff will talk to the participant and provide a referral for additional follow-up and/or medical evaluation for depression.
Weight loss \geq 2% in four weeks during intervention period	Participant will be referred to the registered dietician for follow-up by telephone.
Weight not obtained at the final PT intervention visit and there is weight loss \geq 5% between baseline and follow-up.	Clinical site PI or clinical site clinician will review participant's weight trajectory, baseline BMI, baseline MNA®-SF score and registered dietician's documentation and, if warranted, will refer the participant to a dietician or medical provider for follow-up of possible poor nutritional status.

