12.1.8 Safety Measures for the Nutritional Intervention

If a participant loses 2% or more body weight in a four-week period, the participant will be referred to the registered dietician for follow-up by telephone. In the event that a weight measurement is not obtained at the last PT visit, the participant's weight at the 16-week follow-up assessment will be compared to his or her baseline weight and, if there is weight loss of 5% or more, the clinical site PI or clinical site clinician will review the participant's weight trajectory, baseline BMI, baseline MNA®-SF score, and registered dietician's documentation and, if warranted based on clinical judgment, will refer the participant to a dietician or medical provider for follow-up of possible poor nutritional status.

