15.6.2 Secondary Aims

Delayed and Sustained Effects. Follow-up will end at 16 weeks post-randomization for those consented under version 10.0 of the protocol. We estimate that there will be approximately 150 participants (not the full 210) for whom the 40-week measure of community ambulation will be available. In addition, based on our experience to date, we estimate that the community ambulation outcome will be indeterminate for 10% of the participants at the 40-week assessment. If we assume a sample size of 150 then there is 64% power for detecting a difference of 20 percentage points at alpha = 0.05 using a two-tailed test.

Effect on Secondary and Tertiary Outcomes. Using a two-sided test with alpha=0.05, a sample of 210 patients with 6.8% loss to follow-up and 12.2% treatment noncompliance will provide

80% power to detect effect sizes of 0.46 SD at 16 weeks, which are considered moderate in size, under the assumption that noncompliers assigned to the PUSH group have an equal mean and standard deviation as patients assigned to the PULSE group. Collection of some outcome measures will end after implementation of protocol version 11.0 (see Section 11:). For these measures, we estimate that there will be approximately 160 participants (not the full 210) for whom the 16-week measure will be available. Under the same assumptions, a sample of 160 will provide 80% power to detect an effect size of 0.53 SD.

Economic Evaluation. Follow-up will end at 16 weeks post-randomization for those consented under version 10.0 of the protocol. We estimate that there will be approximately 150 participants for whom the full 40-week follow-up will be available. Assuming a mean SF-6D score of 0.62 in the PULSE group and between-subject standard deviation of 0.10 (based on unpublished data from the fourth BHS cohort study), and assuming that non-compliers assigned to the PUSH group have an equal mean and standard deviation as patients assigned to the PULSE group, a sample size of 75 per group will allow us to detect a between-group difference in means of 0.055 with 80% power and using a two-sided 0.05-level test.

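### Minor safety gap: the 5%-from-baseline weight review applies only when the last PT weight is missing, so gradual loss above 5% can pass unflagged when weights are complete; 11.2 also marks follow-up weight as eliminated

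*Protocol*

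**What the plan says.** The current protocol has two weight-loss rules, given in 9.2, 12.1.8 and Table 2 (section 12.1.2).

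- **Interval rule.** A loss of 2% or more in four weeks leads to a telephone consultation with the dietician, whether or not the loss was intended. On schedule, 10.6.2 says: "Weight will be monitored by the PTs every four weeks during the 16-week intervention period using a standard digital scale". The Version 12.0 entry in the Summary of Modifications describes the comparison as made "between weight assessments performed every four weeks in the course of the intervention visits".
- **Cumulative rule.** The week-16 assessment weight is compared with baseline, and "if there is weight loss of 5% or more, the clinical site PI or clinical site clinician will review" the participant's records, with referral at their discretion. In 9.2 this is conditional: "In the event that a weight measurement is not obtained at the last PT visit". Section 12.1.8 carries the same condition. The Table 2 alert reads "Weight not obtained at the final PT intervention visit and there is weight loss", with the 5% threshold following.

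Version 12.0 removed the follow-up referral based on the MNA-SF. Its stated reasoning is that baseline screening together with "monitoring weight loss throughout the intervention period (the second strategy) will be sufficient". Section 10.4.9 adds: "This measure will not be collected at follow-up for participants consented under protocol version 12.0 or later". Table 2 has no MNA-SF alert.

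On follow-up weight, 10.1.1 requires it at each follow-up visit, and 9.2, 12.1.8 and Table 2 depend on it. Section 11.2 lists weight only in a combined line with quadriceps strength and marks that line as dropped in Version 11.0. Section 10.3.3 drops the strength measure only.

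**The concern.** The 5% review was written as a substitute for a missing last PT weight, but it asks a different question from the rule it replaces. The 2% rule looks at one interval; the 5% rule looks at total change from baseline. As written, a participant gets the cumulative check because a measurement was missed, not because of how much weight was lost. Two participants with the same weight course can be handled differently, and the one with the more complete record has the weaker cumulative check.

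With the MNA-SF referral gone, the 2% rule is the only weight or nutrition trigger left for participants with complete PT weights, and it does not look at cumulative loss. What is at stake is end-of-intervention referral for possible poor nutrition, in a population that 12.1.7 describes as frequently at risk of malnutrition. The primary outcome, the sample size and the error rates are not involved.

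The 11.2 list is a separate and smaller matter. Staff working from that list alone could leave out the week-16 weight on which the existing backstop depends.

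**Working it through.** The plan gives no figure to reproduce. The check is compound-loss arithmetic on the plan's own thresholds.

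**Inputs**
- Interval trigger: 2% in four weeks (9.2, 12.1.8, Table 2).
- Cumulative threshold: 5% from baseline (same places).
- Number of compared intervals, k. Sixteen weeks of four-weekly weights give k = 4 if the baseline weight is the first reference. They give k = 3 if only PT weights at weeks 4, 8, 12 and 16 are compared with each other. The text does not settle this, so both are shown and k = 4 is treated as an assumption. Under k = 3, any loss before the first PT weight is outside the 2% rule.

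**Largest total loss with no interval reaching 2%:** just under 1 − 0.98^k
- k = 4: 1 − 0.98^4 = 0.0776, just under 7.8%
- k = 3: 1 − 0.98^3 = 0.0588, just under 5.9%

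Both exceed 5%, so the gap exists under either count.

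**Smallest steady loss per interval that reaches 5%:** 1 − 0.95^(1/k)
- k = 4: 1 − 0.95^(1/4) = 0.0127, or 1.27%
- k = 3: 1 − 0.95^(1/3) = 0.0170, or 1.70%

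Steady losses from these values up to just under 2% per interval reach 5% with no trigger.

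**Examples**
- 1.5% in each of four intervals: 1 − 0.985^4 = 0.0587, a 5.9% loss
- 1.8% in each of three intervals: 1 − 0.982^3 = 0.0530, a 5.3% loss
- An assumed 150 lb at baseline, losing 1.9% per interval over four: 147.2, 144.4, 141.6 and 138.9 lb, a 7.4% total loss. With the week-16 PT weight recorded, no trigger is met. With that weight missing and the same weight found at the assessment, the case goes to clinician review.

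**Unflagged loss in kilograms (body weights assumed)**

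| Baseline | k = 4: 5% to 7.76% | k = 3: 5% to 5.88% |
|---|---|---|
| 50 kg | 2.5 to 3.9 | 2.5 to 2.9 |
| 60 kg | 3.0 to 4.7 | 3.0 to 3.5 |
| 70 kg | 3.5 to 5.4 | 3.5 to 4.1 |

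**How many participants.** The number in the gap cannot be derived from the documents. One related bound can. For measures dropped in Version 11.0, 15.6.2 says "we estimate that there will be approximately 160 participants (not the full 210) for whom the 16-week measure will be available". Version 12.0 came later, so at most about 210 − 160 = 50 participants are consented under it and have no follow-up MNA-SF. This bounds missing MNA-SF data; it does not count missed referrals.

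**Could the 2% rule be read as cumulative?** Section 9.2 also says the rule covers anyone losing 2% or more of body weight. In context, that sentence makes intent to lose weight irrelevant. The preceding sentence in 9.2, together with 12.1.8 and Table 2, ties the 2% to four weeks.

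**The case against.** The strongest reply is that this is a choice between thresholds. Version 12.0 was a deliberate simplification with a stated reason. The 5% review was introduced only to cover a missing weight, so no general cumulative check was lost, and nothing in the protocol promises one. The 2% rule is already strict. With three intervals, steady loss must average between 1.70% and 2% to escape; at an assumed 60 kg that is within 60 × (0.020 − 0.017) = 0.18 kg of the trigger at every weighing. The 7.8% ceiling needs the baseline weight as first reference, which the Version 12.0 summary does not suggest. The review comes at week 16, when participation ends for those consented under Version 10.0 or later, and leads only to discretionary referral. Every participant has dietician contact at the start and is scheduled for PT visits twice a week. The number affected could be zero. On 11.2, the combined line may be the name of a form, and the intent is clear from other sections. If that form was in fact dropped, weighing everyone at week 16 might be extra work.

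Most of this stands, and it is why the point is minor. It does not explain why a clinician's look at total loss should depend on a missed measurement. The protocol itself set 5% as the loss that merits review, so applying it to everyone brings in no outside standard. The extra-work argument is weak because 10.1.1 already requires the follow-up weight. Using the last PT weight as a fallback would compare a home-visit weight with a clinic weight, which is tolerable for a screen that leads to record review.

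**Conclusion.** The concern holds as a minor safety-monitoring gap. With complete PT weights and no interval at 2% or more, a total loss from 5% to just under 5.9% (three intervals) or just under 7.8% (four intervals, assuming baseline is the first reference) meets no trigger. That a gap exists does not depend on the interval count; its width does. No trigger does not mean no oversight, since dietician and PT contact continue and clinicians may act on judgement.

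The 11.2 entry is a genuine contradiction in a list, but its intent is evident and it does not cause the trigger gap. The main conclusion does not rest on it.

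**What to change.** - **9.2, 12.1.8 and the Table 2 row:** remove the condition that the last PT weight is missing. For every participant, compare the week-16 assessment weight with baseline, using the last PT weight if the week-16 weight is missing. Keep the 5% threshold, the PI or clinician review and the discretionary referral. Leave the 2% rule unchanged.
- **11.2:** list weight as still measured and put the elimination mark on quadriceps strength only, to agree with 10.1.1, 10.3.3, 9.2 and 12.1.8.

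The cost is wording in two sections and one table row, plus one mark in a list. No measurement is added, because 10.1.1 already plans the baseline and week-16 weights. The downside is a few more record reviews for the site PI or clinician.

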9.3 PUSH Intervention

This intervention is based on improving specific precursors to community ambulation by addressing endurance with continuous upright exercise for 20 minutes in duration; function such as walking, standing from a chair, and stair negotiation; muscle performance by exercising to enhance lower extremity strength and power in functionally relevant muscles moving through locomotion-appropriate movements and ranges; and balance by performing unilateral activities and activities with decreased base of support. These components of exercise will be woven together into one program that minimizes participant burden. By the end of the first eight weeks participants will be instructed to complete the endurance component independently one to two times/week by walking for a similar duration and intensity as they have been doing with the PT during the supervised visits.

The strength components of the muscle performance intervention will be performed using a portable progressive resistive exercise device (Shuttle® MiniPress, Contemporary Design Company, [name]). The device has six latex bands each with a starting load equal to approximately seven pounds. At full excursion one band can provide approximately 15 pounds of force. These bands provide the resistance and are attached to the machine by a slotted bar on the frame. Inserting more bands into the slotted bar increases the resistive load for the participant. A progress monitor strip is located on the top of the machine frame. Strips indicate resistance by showing distance that the load is moved. The resistance numbers indicate the force for one band as the carriage is moved. When more than one band is used, the values will be added.¹³⁷

Muscle performance will focus on bilateral hip extensors, hip abductors, knee extensors, and plantar flexors because of their role in function, specifically gait and transfer activities.¹³⁸⁻¹⁴⁰ Hip and knee extensor muscle will be trained to work hard and fast during the leg press motion since this mimics the functional activity of rising from a chair or going up a step. Hip abductors will be trained in 5° of adduction and to 10-15° of abduction. Fifteen degrees of movement was chosen because it approximates the 8° of motion associated with gait and takes into account variations in hip positions while standing.¹⁴¹ Hip extension will also be trained in standing from 35° of flexion to extension to a neutral position. This ROM approximates the time in the gait cycle when the gluteus maximus shows the highest muscle activity, i.e., from heel contact through 20% of stride.¹³⁹ Plantar flexors will be strengthened in standing against body weight⁷⁷ because of their role in the push-off phase of gait and the strong association of plantar flexion power and walking speed.^{77,138-142} The intensity of strength training will be determined during Day 1 of intervention at the participant's residence. The PT will determine the amount of resistance the participant can push against so that s/he can complete a maximum of eight repetitions (eight repetitions maximum (RM) or 8-RM). 8-RM was chosen because it is strongly related to the 1-RM¹⁴³ and determining the 8-RM will allow the PT to know the training intensity without further sub-calculations (e.g. 80% of the 1-RM). Studies have shown that the 8-RM is more effective than training at 10-RM or 2-RM⁸⁸ yet is not so aggressive that it is associated with injuries.^{144,145} This protocol has been used safely and effectively in elders^{21,73,74,77,140,146} and specifically in persons post-hip fracture.^{29,70} For the first visit, participants will be tested to find the load associated with an intensity of 8-RM. During the second session, participants will perform 2 sets of 8 repetitions at the 8-RM intensity. From the third session through the remainder of the program, participants will perform 3 sets of 8 repetitions at an intensity of the 8-

Figure 3. Shuttle Device (arrows indicate direction of lower extremity motion)

RM. The PT will provide strong verbal encouragement during each repetition for the participant to move as “fast and

as hard as possible” during the concentric phase and to move slowly and in a controlled way in the eccentric phase. Intensity will be reviewed every two weeks.

The participants will be supine for two exercises: the combination of hip and knee extension exercise (leg press) and the hip abduction exercise (Figure 3a & 3b). The device will be placed on the bed or floor (if the participant is able to be assisted safely to and from the floor) so that the participant’s foot will rest on the footplate and the hip will be flexed to 90°. The participant will push the leg out into full hip and knee extension against the pre-determined resistance. For the hip abductors, the participant will start in 5° of adduction and move 15° into abduction. The participant’s foot will be strapped to the footplate as the participant moves the leg outward.

Balance and strength will be addressed with two additional exercises performed in standing. Balance will be addressed by asking the participant to perform one-legged activities or to stand upright with a decreased base of support. The first exercise that combines balance training and strength training will be standing hip extension (Figure 3c). The leg will be flexed approximately 35° of flexion and the participant will extend to neutral position. Upright balance will be challenged as the participant moves the carriage of the exercise device with one leg as the other leg maintains stability.

The second exercise that combines balance and strength training will be standing plantar flexion. Initially, participants will be asked to decrease their standing base of support by rising onto the balls of feet. This exercise also strengthens the plantar flexors. Balance and strength will be progressively challenged by advancing the activity to unilateral heel raises. For hip extension and plantar flexion, the person may hold lightly onto an assistive device for balance or support. The PT will encourage the participant to use less external support for balance during each session. Resistance (load in pounds) and repetitions for each exercise performed will be recorded in a training log.²⁹

HR will be measured by palpation of the radial artery recorded every five minutes and it will be averaged over 20 minutes of continuous exercise. The PT will calculate the HR training zone based on the heart rate reserve (HRR) method (HR max-HR rest) multiplied by 50% and then added to HR rest. HR max will be calculated as 220 minus the participant’s age. This prescription is consistent with moderate intensity exercise and has been shown to increase aerobic capacity in elders.¹⁴⁷⁻¹⁴⁹ If the person is taking medication that controls heart rate (e.g., beta-blockers), Borg’s Rating of Perceived Exertion (RPE) scale will be used.¹⁵⁰ The training intensity using the RPE scale will be “moderate” work as consistent with a 3-5 on the 0-10 scale.

The endurance intervention will begin initially with two to three minutes of continuous upper and lower extremity AROM with the participant sitting. These exercises are intended to increase the participants’ HR or exertion closer to the target zone. The participant will then be asked to walk on level surfaces and up and down one or more steps, if able and available, to keep the HR within the training zone for 20 minutes. The PT can also engage the participant in additional exercises such as upper and lower extremity AROM exercises to keep the HR elevated. The

target HR will be 30% of HRR in the first week of the program, 40% of HRR in the second week, and 50% of HRR in weeks 3 through 16.

